An exciting application for EIT is to monitor the regional and global distribution of tidal ventilation during positive pressure ventilation. Clinical studies have shown the value of EIT to quantify the effects of suctioning and ventilator disconnection, during placement of double-lumen endotracheal tubes, and to detect an incidental pneumothorax or pulmonary edema. Most importantly is the ability of EIT to assess lung recruitment and derecruitment as well as to assess for alveolar overdistension in an attempt to provide a lung protective ventilation strategy.

EIT has also been applied to study the effects of various devices used to provide noninvasive ventilation. Noninvasive ventilation (NIV) is a form of mechanical ventilation which does not involve placement of and attachment to an artificial airway. Rather the ventilator is attached to the subject via a face mask or other noninvasive interface. Pelosi evaluated three devices used to provide a form of NIV, continuous positive airway pressure (CPAP), that create airway pressure using different methods (high flow CPAP, low-flow CPAP and an ICU ventilator) and detected differences in breathing pattern, end-expiratory lung volume (EELV) and airway pressures between the devices. Andersson evaluated three CPAP systems using EIT in 14 healthy volunteers. They found different airway pressure profiles resulting in varying levels of EELV and noted that EELV increased more in ventral lung regions with increasing CPAP levels, independent of the system used, and a redistribution of tidal ventilation toward dorsal lung regions. EIT may prove useful to optimally adjust NPPV settings to improve ventilation and oxygenation.

Our plan is to perform a study similar to that described by Andersson as an initial project on the use of EIT.

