## **2.0 Hypothesis**

We hypothesize that the distribution of ventilation and EELV in healthy adult subjects will not be different when NPPV is applied via different devices set to identical pressure settings. Also, when applying increasing NPPV pressures, the distribution of ventilation will shift from the ventral to dorsal regions and be similar between devices.

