## **4.0 Study Procedures**

4.1 Written informed consent will be obtained on all subjects prior to enrollment in the study and before any research procedures are performed. Subjects can withdraw from the study at any time.

4.2 Subjects will undergo testing by applying NPPV via 2 different BiPAP devices that are currently used in standard of care for patients at the University of Michigan Health System. The decision of which device to begin with will be determined by random allocation of a coin toss.

4.3 BiPAP Systems:

4.3.1 The Resironics V-60 (Phillips, Carlsbad CA) device is continuous high flow, blower type of generator.

4.3.2 The Drager V-500 (Drager Medical, Lubeck, Germany) is our primary critical care ventilator that has a specific NPPV mode.

- 4.4 EIT System: The Drager PulmoVista 500 EIT system (Drager Medical, Lubeck, Germany) consists of an electrode belt connected to the EIT monitor. Before using the system it will be reviewed and approved for use by our Biomedical Department.
- 4.5 Subjects will be placed in the supine position. This position will be maintained for the entire procedure. An electrode belt will be placed on the subject at the 5th intercostal space and connected to the EIT monitor. Prior to initiating a study session, the EIT system will be calibrated per manufacturer's instruction.
- 4.6 Each study device will be applied in the following manner:
  - 4.6.1 Four steps (series of device setting changes) will be applied, as such:
    - 4.6.1.1 A baseline will be established breathing without the NPPV mask attached
    - 4.6.1.2 Following mask attachment, a pressure support of 0 cm H2O and PEEP of 5 cm H2O will be applied, then
    - 4.6.1.3 A pressure support of 5 cm H2O and PEEP of 5 cm H2O, then
    - 4.6.1.4 A pressure support of 5 cm H2O and PEEP of 10 cm H2O.
  - 4.6.2 Each step will consist of a 5-minute stabilization period, and then readings will be taken over the next two minutes before proceeding to the next step.
  - 4.6.3 Following all four steps with the initial device, the second device will be applied and steps 1-4 repeated.
- 4.7 Primary Outcomes: Global Tidal Variation (see figures 4-6)
- 4.8 Secondary Outcomes:
  - 4.8.1 Regional Tidal Variations
  - 4.8.2 Global and Regional changes in End-Expiratory Lung Impedance (EELI)
- 4.9 Exploratory Outcomes:

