  - 4.9.1 A pneumotachometer (NM3 monitor, Phillips Healthcare, Andover MA), will be placed between the mask and inspiratory hose and the following measurements obtained: respiratory rate, tidal volume, peak inspiratory

pressure, PEEP. A pulse oximeter (RAD8, Masimo, Irvine CA) will provide SpO2 and heart rate.

- 4.9.2 Change in regional and global distribution in subjects with a BMI less than or greater than 25 kg/m^2
- 4.9.3 Change in global and regional distribution for subjects at 0 degrees, 45 degrees, and 90 degrees' body positions.

4.10 In addition to device testing, baseline demographics such as age and gender will be recorded for each subject.

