## 5.0 Statistical Analysis

A two-way ANOVA will be the first step of analysis to determine the influence of the BiPAP systems on the NPPV. Regional distribution of tidal volume will be analyzed using four ventral to dorsal regions of interest (ROI) by EIT. The relative distribution of tidal volume between regions will be displayed as a percentage. Regional change in end-expiratory lung impedance (EELI) will be similarly expressed as a percent for each ROI. These parameters will be treated as functions of each individual step outlined in 4.6, with particular attention paid to the pressure support and PEEP. Values will be presented as mean  $\pm$  standard deviation and initial comparisons will be made using paired *t*-tests against baseline. Given the factorial design of experiment, if further analysis becomes warranted, a multivariate ANOVA will be utilized to determine the time, pressure, and total tidal volume relationship to relative distribution of tidal volume within the regions of interest. Potential confounding parameters such as patient size, weight, and health status will be screened in a similar manner.

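### The only primary outcome, Global Tidal Variation, is a whole-lung total that cannot test either part of the hypothesis, and Section 5.0 does not name it as a response

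*Combined protocol and SAP*

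**What the plan says.** Section 2.0 has two parts. The first is that, at identical pressure settings on the two devices, "the distribution of ventilation and EELV in healthy adult subjects will not be different". The second is that, as pressure rises, "the distribution of ventilation will shift from the ventral to dorsal regions and be similar between devices".

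Section 4.7 gives a single primary outcome: "Primary Outcomes: Global Tidal Variation (see figures 4-6"). Section 4.8 lists as secondary the regional tidal variations (4.8.1) and "Global and Regional changes in End-Expiratory Lung Impedance (EELI") (4.8.2).

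Section 5.0 opens with its only comparison between devices: "A two-way ANOVA will be the first step of analysis to determine the influence of the BiPAP systems on the NPPV". It then describes the regional distribution of tidal volume over four ventral-to-dorsal regions of interest (ROIs) and the regional change in EELI, both as percentages and by step. The paired t-tests are against baseline, not between devices. Global Tidal Variation is not mentioned. Total tidal volume appears once, as an explanatory term in a multivariate ANOVA that is run only if further analysis seems warranted.

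The Figure 4 caption gives the global value as 100%, beside a percentage for each ROI, and also lists a global impedance waveform.

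**The concern.** The hypothesis is about where the air goes and how much lung volume remains at end-expiration. The primary outcome is the size of the whole-lung tidal swing. Two devices could agree on that swing and still ventilate different regions or hold different end-expiratory volumes. They could also differ on it while distributing air identically.

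Two things are at stake. A non-significant comparison of the global total could be read as showing no difference in distribution, which it cannot show. And because 5.0 ties no named response to the device comparison, the conclusion could come to rest on whichever outcome looks favourable once the data are seen.

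**Working it through.** The plan states no SD, significance level, power, effect size or equivalence margin, so it has no figure of its own to reproduce. The first step compares the text. The other two are illustrations on stated assumptions.

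**1. Hypothesis against outcomes and analysis**

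| Part of 2.0 | Outcome that measures it | Rank | Treatment in 5.0 |
|---|---|---|---|
| Distribution alike between devices | Regional tidal variation (4.8.1) | Secondary | Described by ROI and step; device comparison not tied to it |
| EELV alike between devices | Change in EELI (4.8.2) | Secondary | Regional change described by ROI and step; same gap |
| Ventral-to-dorsal shift, alike between devices | Regional tidal variation by step (4.8.1) | Secondary | By step; device-by-step effect not stated |
| None | Global Tidal Variation (4.7) | Primary | Not named |

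**2. Can the global total carry the information?** Take invented tidal variation in four ROIs, ventral to dorsal:

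- Device A: 15 + 35 + 35 + 15 = 100; dorsal share (35 + 15)/100 = 50%.
- Device B: 5 + 25 + 40 + 30 = 100; dorsal share (40 + 30)/100 = 70%.

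The totals are equal while the dorsal share differs by 20 points. This holds on any scale. If the global value were recorded as the 100% in the Figure 4 caption, it would be constant. If it is an impedance amplitude, it varies, but it still says nothing about regions or end-expiratory level.

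**3. What a regional primary outcome would offer with the planned sample.** Inputs: n = 20 (Section 3.1), and each subject's difference between devices in dorsal share, averaged over the three mask-on steps. Assumed: two-sided 5% level; SD of that paired difference 5, 8 or 10 points; a difference of interest, and a margin, of 5 points.

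- Half-width of the 95% CI = t(0.975, 19 df) × SD/√20 = 2.093/4.472 × SD = 0.468 × SD.
- Power for a true 5-point difference: noncentral t on 19 df with noncentrality 5√20/SD.
- Chance that the CI lies wholly within ±5 when the devices are truly equal: numerical integration over the sample variance.

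| SD | 95% CI half-width | Power for 5 points | Non-significant despite a 5-point difference | 95% CI within ±5 if equal | 90% CI within ±5 if equal |
|---|---|---|---|---|---|
| 5 | 2.34 | 98.9% | 1.1% | 97.7% | 99% |
| 8 | 3.74 | 75.5% | 24.5% | 51.3% | 71% |
| 10 | 4.68 | 56.5% | 43.5% | 18.2% | 39% |

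The 90% column is the usual criterion of two one-sided tests at 5%; the 95% column is stricter. Fitting device order leaves 18 df and changes little: half-width 0.470 × SD, power 98.8%, 75.3% and 56.2%.

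If the devices do not differ in the global total, a 5% test on that total rejects 5% of the time, however large the regional difference.

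**The case against.** The strongest reply is that little depends on the label. The plan has no sample size calculation, alpha allocation, interim look or decision rule linked to the primary outcome. The study is an initial project on healthy volunteers, partly to learn the equipment (1.0 and 7.0), and 5.0 does analyse regional distribution and regional EELI. This stands as a limit on the consequence: the hypothesis remains testable and no data are lost.

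A second reply is that the ANOVA is naturally read as device by step on the regional parameters, since 5.0 refers to a factorial design and to the steps in 4.6. That may be what was meant, but the text does not say so, and on that reading the declared primary outcome has no analysis at all.

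Third, 4.7 points to Figures 4-6, which also cover regional distribution and end-expiratory change. But 4.8 lists those measures separately as secondary, so the pointer does not promote them. The images are not available here and may define a scale for the global value; no scale would give it regional content.

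Fourth, the plan speaks of using EIT to "monitor the regional and global distribution of tidal ventilation during positive pressure ventilation" (1.0) and, in 4.9.2, of "Change in regional and global distribution in subjects with a BMI" above or below a cut-off. This is loose wording: a single total has no distribution across regions.

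Two smaller points are fair. Total tidal volume in 5.0 may mean the pneumotachometer reading of 4.9.1 rather than an EIT quantity, so its explanatory role is only supporting evidence. And the precision figures above describe a replacement outcome on assumed SDs; they do not measure the defect itself.

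**Conclusion.** The concern holds. Followed as written, the plan yields a primary result that cannot answer Section 2.0, and it gives that primary outcome no stated analysis. This is a fault in how the outcomes are ranked and in the response named for the ANOVA, not a loss of data. It should be fixed, but it does not undermine the study. The conclusion rests on the text alone and on the fact that a sum does not determine its parts.

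The precision figures depend on the assumed SDs and the assumed 5 points. Across that range, 20 pairs run from ample to weak for a 5-point regional difference (power 99% down to 56%). A non-significant result therefore should not be taken as showing equality. A global total still serves the general device comparison in 7.0 and is worth keeping.

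**What to change.** Make these changes as a dated amendment before the data are analysed. The documents do not say whether that point has passed; if it has, the change must be reported as post hoc.

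- **4.7:** make one named regional summary of tidal variation primary, for example the dorsal share (the sum of the two dorsal ROI percentages).
- **4.8:** name change in global EELI from the same device run's baseline as the first key secondary outcome (the EELV part), and the step and device-by-step effects on the regional summary as the second (the shift). Keep Global Tidal Variation as a secondary outcome, defined as tidal impedance amplitude relative to the same run's mask-off baseline. Each run has its own baseline, because under 4.6.3 "the second device will be applied and steps 1-4 repeated".
- **5.0:** replace the present ANOVA response with these outcomes. Compare devices within subject across the three mask-on steps and report the average device difference with its 95% CI. State that a non-significant test will not be read as showing no difference. If equivalence (7.0) is to be claimed, fix the margin for the primary outcome in advance, say which CI level applies, and judge by whether the CI lies inside the margin.

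The cost is redrafting of 4.7, 4.8 and 5.0, with no new subject, procedure or measurement. The downside is that a declared primary outcome changes, while EELV and the pressure shift remain secondary.

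A lighter alternative also removes the contradiction: keep Global Tidal Variation as primary, define its scale, name it in 5.0 and rewrite 2.0 to match. It too costs only redrafting, but it gives up distribution and EELV as the primary question. The choice is the sponsor's.

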## **3.0 Subject Selection and Enrollment**

3.1 Subjects: Twenty adult healthy volunteers will be recruited for this study. They will be solicited from within the University of Michigan Health System (e.g. students, staff, and employees). No financial incentive will be provided.

3.2 Inclusion Criteria:

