3.2.1 Age 18 years or older

3.3 Exclusion Criteria:

3.3.1 Use of a cardiac pacemaker, an implantable cardioverter-defibrillator (ICD) or any other active implants [electrical current may interfere with EIT signal]

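### Minor, cheap improvement: analyse BMI as a continuous variable in the exploratory analysis instead of splitting 20 volunteers at 25 kg/m², and assign a BMI of exactly 25 to a group

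*Combined protocol and SAP*

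**What the plan says.** Among the items under "4.9 Exploratory Outcomes", section 4.9.2 of the combined protocol and SAP gives "Change in regional and global distribution in subjects with a BMI less than or greater than 25" kg/m². No reason for the cut is stated.

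Section 3.1 sets the size: "Twenty adult healthy volunteers will be recruited for this study". The one inclusion criterion in section 3.2 is "Age 18 years or older", and the exclusion criterion concerns active implants. There is no BMI quota or stratification, so the sizes of the two groups are left to chance.

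Section 5.0 names no model for the BMI outcome. Its nearest statement is "Potential confounding parameters such as patient size, weight, and health status will be screened in a similar manner", which follows the description of the ANOVA and paired t-tests and does not say whether body size enters as a continuous or a grouped variable.

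Section 4.10 states that "baseline demographics such as age and gender will be recorded for each subject". Height, weight and BMI are not named.

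**The concern.** Splitting a continuous measure in two treats all subjects on one side of the cut as alike, and treats subjects just either side of it as different. With 20 subjects the plan has little information to spare. With no control over recruitment by BMI, one of the groups could also be very small.

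BMI is the only subject characteristic by which the plan defines an outcome. Each subject is tested on both devices and at all steps (section 4.6), so a fixed trait such as BMI cannot confound those within-subject comparisons. It can only modify the response. Section 4.9.2 is where such modification would be seen, and a split makes a gradual relation easier to miss.

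The wording also leaves a BMI of exactly 25 without a group.

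**Working it through.** The documents state no alpha, effect size, standard deviation or BMI distribution, so there is no figure of the plan's own to reproduce.

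**Inputs from the documents:** n = 20 (section 3.1); cut at 25 kg/m² (section 4.9.2); no stratification by BMI (section 3.0).

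**Assumptions:** two-sided 5% test; BMI distributions and effect shapes as stated at each step.

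**1. Information kept by the split.** The share kept is the squared correlation between BMI and the indicator of being above the cut. For normal BMI and a linear effect this is φ(c)² / [p(1−p)], where p is the share below the cut, c is the matching normal quantile and φ is the normal density.

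| Split | Calculation | Kept | Lost | Equivalent subjects of 20 |
|---|---|---|---|---|
| 50:50 | 0.399² / 0.25 | 0.637 | 36% | 12.7 |
| 60:40 | 0.386² / 0.24 | 0.622 | 38% | 12.4 |
| 70:30 | 0.348² / 0.21 | 0.576 | 42% | 11.5 |
| 80:20 | 0.280² / 0.16 | 0.490 | 51% | 9.8 |

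**2. Other BMI shapes, linear effect, simulated.**
- Lognormal, median 23 to 27, log-SD 0.12 to 0.25: loss 37% to 50%.
- Uniform, cut at the middle: loss 25%.
- Two equal clusters at 22 and 28, within-cluster SD 1, 2 and 3: loss 10%, 25% and 32%.

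**3. Power at n = 20** (40,000 simulated trials, one outcome value per subject, normal BMI with SD 4).

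| True correlation | Continuous, linear truth | Split, linear truth, mean BMI 25 (about 50:50) | Split, linear truth, mean BMI 23 (about 70:30) | Continuous, step at 25, mean BMI 25 | Split, step at 25, mean BMI 25 |
|---|---|---|---|---|---|
| 0.4 | 43% | 28% | 26% | 29% | 44% |
| 0.5 | 64% | 43% | 40% | 44% | 66% |
| 0.6 | 84% | 61% | 56% | 63% | 87% |

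Another run of the 50:50 case at correlation 0.5 gave 44%, so 43% to 44% is the figure to carry. Under a linear truth the continuous analysis has about 20 points more power at that correlation (64 − 44). Under a step at 25 the order reverses by a similar amount (66 − 44 = 22 points).

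**4. Group sizes left to chance** (binomial, n = 20). The probability that one group has 5 or fewer subjects is 4% if half of the volunteers lie below 25, 13% if 60% do, 42% if 70% do and 80% if 80% do. For a true group difference of 1 SD (normal approximation), power is 61% with groups of 10 and 10, 49% with 15 and 5, and 36% with 17 and 3.

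**5. A BMI of exactly 25** (normal, mean 24 to 25, SD 3 to 4). Recorded to one decimal, about 1% of subjects would be at 25.0, so the chance of at least one in 20 is 18% to 23%. Rounded to whole units, about 10% to 13% would be at 25, and the chance is 87% to 94%.

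**The case against.** Several stronger readings are tempting, and the documents do not support them.

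- **That the split certainly wastes a third or more of the information.** This needs roughly normal or mildly skewed BMI and a linear effect. The documents give neither, and other plausible shapes lose 10% to 32%.
- **That a continuous term is free and the split gains nothing.** A slope assumes approximate linearity, can be driven by one or two extreme BMI values among 20 subjects, and has clearly less power if the effect is a step at 25. The documents suggest no such step, but they do not rule one out.
- **That subjects at exactly 25 are excluded.** No text excludes them. A missing equality sign is the likelier explanation. The gap still has to be closed before the groups are formed.
- **That all within-group variation will be ignored.** Section 4.9.2 defines the outcome by group, but section 5.0 fixes no test for it and leaves room for body size as a continuous covariate. That room is not a commitment: the sentence treats size and weight as confounders and states no coding.

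It is also fair to say that the power figures concern one outcome value per subject. They fit a single contrast, such as the change between two steps. They do not give the power of a full repeated-measures model with several interactions, or allow for testing global values and four regions. At a correlation of 0.4 neither analysis is adequate (43% against 28%).

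Finally, this is an exploratory item in a healthy-volunteer study. That limits the weight of the point but does not remove it, because the better analysis needs no more subjects than the planned one.

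**Conclusion.** The point holds as a minor improvement. Section 4.9.2 defines its BMI outcome by an unexplained cut at 25 in 20 unstratified volunteers and leaves one value unassigned. Section 5.0 does not repair this.

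With roughly normal BMI and a roughly linear effect, the split keeps between about half and two thirds of the information, depending on how evenly the groups fall. Power at a correlation of 0.5 then drops from about 64% to between 40% and 44%. These figures rest on assumptions outside the documents. The loss is smaller for uniform or clustered BMI, and the preference reverses for a true step at 25. Without a stated reason to expect a step there, the continuous analysis is the better default.

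The primary outcome, global Tidal Variation, and the comparison of the two devices do not depend on this choice.

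**What to change.** - In section 5.0, make continuous BMI the main exploratory BMI analysis of change in global and regional distribution. Include BMI and its interactions with step and device, in a model that respects the repeated measures on each subject.
- State how linearity and influential values will be checked: a scatter plot for each main contrast, and a repeat of the analysis without the most extreme BMI values.
- Report these analyses as exploratory estimates with confidence intervals, since several interactions and regions are examined.
- In section 4.9.2, keep the groups for description only, as below 25 and 25 or above. If the sponsor has a reason to expect a threshold at 25, state it there.
- In section 4.10, name height and weight as recorded data.

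**Cost:** revised wording and two simple measurements that the planned split needs in any case. No extra subjects or visits are required, and a linear BMI term uses one degree of freedom, as the split does. The price is the linearity assumption, sensitivity to extreme BMI values at n = 20, and lower power if the true effect is a step at 25.
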